9.6. Multiple Comparisons and Multiplicity

A fixed-sequence testing procedure will be employed to control the overall Type I error rate at the 2-sided 0.05 level for the co-primary endpoints. The sequential order of comparisons will be as follows:

1. 1-hour postdose percent predicted FEV₁ comparing FS MDPI 50/12.5 mcg versus Fp MDPI 50 mcg
9. Trough percent predicted FEV₁ comparing Fp MDPI 50 mcg versus placebo
10. Trough percent predicted FEV₁ comparing Fp MDPI 25 mcg versus placebo

Each test will be 2-sided and performed at the 0.05 level of significance. However, if a test is not significant at the 2-sided 0.05 level, no further tests will be performed.

Taking into consideration that this is the very first study that utilizes the handheld device in a large Phase 3 study in a pediatric asthma patient population (4 to 11 years of age), an unplanned blinded sample size reassessment was conducted. Since the adjustment to sample size was based on blinded standard deviation, no adjustment to the multiplicity control is warranted.

Multiplicity control for the secondary endpoints and the sequential order of the secondary endpoints will be described in the statistical analysis plan.

No multiplicity adjustments will be made for other efficacy analyses.

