2.4. Sample Size and Power Considerations

Sample size and power calculations are driven by demonstrating superiority of FS MDPI 50/12.5 mcg twice daily over Fp MDPI 50 mcg twice daily in change from baseline in 1-hour postdose percent predicted morning FEV₁ at week 12 and the superiority of Fp MDPI 50 mcg twice daily over placebo in change from baseline in percent predicted trough morning FEV₁ at week 12.

For the superiority comparison of FS MDPI 50/12.5 mcg twice daily versus Fp MDPI 50 mcg twice daily, assuming that the change from baseline in 1-hour postdose percent predicted morning FEV₁ at week 12 is analyzed using an ANOVA model with only a single factor of treatment group, the following assumptions were made:

- The initial assumed common standard deviation (SD) was 9.3% and the true treatment difference was 4.5% between FS MDPI 50/12.5 mcg twice daily and Fp MDPI 50 mcg twice daily. This assumption was based on data collected in previous Teva studies with the same Fp MDPI and FS MDPI products in adult asthma patients who completed the 12-week treatment period and based on office-based spirometry.
- The initial power was 97% at a 2-sided significance level of 5%.

For the superiority comparison of Fp MDPI 50 mcg twice daily versus placebo, assuming that the change from baseline in percent predicted trough morning FEV₁ at week 12 is analyzed using an analysis of variance (ANOVA) model with only a single factor of treatment group, the following assumptions were made:

- The initial assumed common standard deviation (SD) was 13.25% and the true treatment difference was 5% between Fp MDPI 50 mcg twice daily and placebo. This assumption was based on data collected in previous Teva studies with the same Fp MDPI product in adult asthma patients and based on office-based spirometry
- The initial power was 85% at a 2-sided significance level of 5%.

Study FSS-AS-30003 is the very first study in which a handheld spirometry device is utilized 1) as the primary endpoint in a Phase 3 study and 2) in a pediatric asthma patient population for a pivotal study of this scale. This made it difficult to predict the actual variability of the data. A blinded sample size reassessment was not planned. Routine blinded data monitoring of this study FSS-AS-30003 revealed that the SD for the overall study population is indeed higher than the initial assumptions. In addition, FEV₁ stability has been monitored closely throughout this study

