(see Clinical Study Protocol FSS-AS-30003 Section 6.1.3 for detail). A number of alerts were determined by the investigators as not related to worsening asthma but rather due to poor patients' effort, which has been challenging in this patient population as young as 4 years of age, despite the rigorous training and coaching provided by the investigators. To ensure the high quality of the FEV₁ data and integrity of the study, an unplanned blinded data quality evaluation and sample size reassessment was conducted. Some of the initial assumptions and the sample size described above were revised to the following:

- For the superiority comparison of FS MDPI 50/12.5 mcg twice daily versus Fp MDPI 50 mcg twice daily, the SD was revised to 22% and the overall mean change from baseline was revised to 6.5% (blinded SD observed after 427 patients completed week 12 of this study (excluding IMPD)) and the power down to 80%.
- With these assumptions, 181 patients per treatment group are required for the 2-sided test of FS MDPI 50/12.5 mcg twice daily and Fp MDPI 50 mcg twice daily.
- For the superiority comparison of Fp MDPI 50 mcg twice daily versus placebo, the SD was revised to 17% and overall mean change from baseline was 5% (blinded SD observed after 434 patients completed week 12 of this study (excluding IMPD) and the power was revised to 80%.
- With these assumptions, 181 patients per treatment group are required for the 2-sided test of Fp MDPI 50 mcg twice daily versus placebo.

Based on current blinded data and assuming a dropout rate of 12%, a total of 824 patients (206 patients per treatment group) will be randomized (initial assumption for dropout rate was 15%).

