4.2. Specification of Baseline Values

In general, the baseline values for efficacy and safety variables are defined as the last observed data before the first dose of study drug, unless otherwise noted.

For data collected daily in electronic patient diaries (ie, daily FEV₁, PEF, asthma symptom scores, rescue medication use, etc.), baseline is defined as the average of daily data recorded in the 7 days before randomization. The prerandomization day consists of the electronic patient diary entries on the evening prior to the RV (TV1) or on the morning of the RV (TV1) for evening or morning FEV₁ and PEF values, respectively. The first postbaseline record is the data collected after the first dose on the evening of the RV (TV1). Patients have to record baseline values on at least 5 out of the last 7 days prior to the RV in order to be randomized, nonetheless, a few patients who were randomized with less than 5 nonmissing values. To eliminate number of missing baseline values, rules for handling missing electronic patient’s diaries are specified below.

Weekly Average Percent Predicted Trough Morning FEV₁ and Trough Morning PEF:

The baseline percent predicted trough morning FEV₁ or trough morning PEF is defined as the average of recorded (nonmissing) percent predicted trough morning FEV₁ or trough morning PEF assessments over the 7 days prior to randomization. The first day before randomization consists of the electronic patient diary entry at **home** on the morning of the RV (TV1). A patient has to record trough morning FEV₁ and trough morning PEF values on at least 5 out of the last 7 days prior to the RV in order to be randomized. In case there are less than 5 non-missing values, the trough morning FEV₁ or trough morning PEF record will include days beyond 7 days prior to the randomization to ensure that the baseline value can be calculated. If a minimum of

5 nonmissing values cannot be satisfied during the entire run-in period (14-30 days), the patient's percent predicted trough morning FEV₁ or trough morning PEF baseline values will be replaced by the overall baseline value.

1-Hour Percent Predicted Trough Morning FEV₁:

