The baseline 1-hour percent predicted trough morning FEV₁ is defined as the predose percent predicted trough morning FEV₁ measurement at the RV (TV1) at the **investigational center**. If the predose FEV₁ measurement is missing or the value is implausible, the baseline weekly at home average percent predicted trough morning FEV₁ will be used. If both, the baseline pre-dose FEV₁ measurement and the baseline weekly average percent predicted trough morning FEV₁ are missing, the baseline trough morning FEV₁ will be replaced by the overall baseline 1-hour value.

Trough Evening PEF:

The baseline trough evening PEF is defined as the average of recorded (nonmissing) trough evening PEF assessments over the 7 days prior to randomization. The first day before randomization consists of the electronic patient diary entry on the evening before the RV (TV1). Five out of the last 7 days nonmissing values are required for a patient to be randomized and to calculate the baseline value. In case the minimum of 5 nonmissing values cannot be satisfied during the entire run-in period (14-30 days), the patient's evening PEF baseline value will include days beyond 7 days prior to the randomization. If a minimum of 5 nonmissing values cannot meet, missing baseline value will be replaced by the overall trough evening PEF value.

Total Daily (24-Hour) Use of Albuterol/Salbutamol Inhalation Aerosol (Number of Inhalations):

Throughout the study albuterol/salbutamol inhalation aerosol will be provided to patients to be used as needed for the relief of asthma symptoms. Patients will record intake (number of inhalations) of rescue medication each morning and evening in the electronic patient diary. An entry of zero inhalations for both morning and evening will indicate a rescue-free 24-hour period.

The baseline value is defined as the average number of inhalations over each 24-hour (day and night) period over the 7 days prior to the date of the first dose. Patients should withhold their rescue medication for at least 6 hours prior to the morning of the RV (TV1), and all other study visits. Five out of last 7 days nonmissing values are required for patient to be randomized. No missing data imputation rule will apply.

Percentage of Rescue-free Days (24-Hour Periods):

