The co-primary endpoint change from baseline in 1-hour postdose percent predicted morning FEV₁ at week 12 will be analyzed using an ANCOVA model with effects due to baseline trough morning percent predicted FEV₁, sex, age, (pooled) investigational center, previous therapy (ICS or NCS), and IMP treatment group. Contrasts for pairwise treatment comparisons of interest will be constructed. The estimated treatment comparisons of interest will be presented together with the 2-sided 95% CI for the difference and the p-value. Missing 1-hour postdose FEV₁ data at week 12 will be handled similarly to the above (see [Appendix A](#) for details).

For patients who completed the treatment period, but with clinically and physiologically implausible data (eg, percent predicted FEV₁ values post-randomization is $\geq 200\%$), imputation will be based on measurements observed at previous weeks and in the same treatment group (this represent a MAR mechanism).

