7. MULTIPLE COMPARISONS AND MULTIPLICITY

7.1. Multiple Comparisons for the Primary Analysis

For the analysis of the co-primary endpoints, a fixed-sequence multiple testing procedure will be employed to control the overall Type I error rate at the 0.05 level, as described in [Table 7](#). Specifically, treatment comparisons will begin with the first primary endpoint, [1] 1-hour postdose percent predicted morning FEV₁ at week 12 at the FS MDPI 50/12.5 versus Fp MDPI 50 mcg. If the resulting p-value is less than 0.05, then the next comparison of interest will be made, according to the direction of the arrow. This process will continue until the point where the p-value is greater than 0.05 at which no further comparisons will be interpreted inferentially.

Taking into consideration that this is the very first study that utilizes the handheld device in a large Phase 3 study in a pediatric asthma patient population (4 through 11 years of age), an unplanned blinded sample size re-assessment was conducted. Since the adjustment to sample size was based on blinded standard deviation, no adjustment to the multiplicity control is warranted.

No multiplicity adjustment will be made for sensitivity analyses of the primary endpoints or subgroups.

Table 7: Multiple Testing Procedures

Sequence	Primary Endpoint	Hypothesis Testing
1	[1] Change from baseline in 1-hour postdose percent predicted morning FEV ₁ at week 12	FS MDPI 50/12.5 mcg BID vs. Fp MDPI 50 mcg BID
		↓
2	[2] Change from baseline in weekly average of the percent predicted trough morning FEV ₁ at week 12	Fp MDPI 50 mcg BID vs. Placebo
		↓
3	[2] Change from baseline in weekly average of the percent predicted trough morning FEV ₁ at week 12	Fp MDPI 25 mcg BID vs. Placebo

FEV₁= forced expiratory volume in 1 second; FS MDPI = fluticasone propionate/salmeterol xinafoate multidose dry powder inhaler, Fp MDPI = fluticasone propionate multidose dry powder inhaler.

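### The lead 1-hour ANCOVA is valid but does not use the 7-day home trough average as a second baseline covariate, so a small and cheap gain in precision goes unused

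*SAP*

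**What the plan says.** SAP 7.1 puts FS MDPI 50/12.5 versus Fp MDPI 50 on the 1-hour endpoint at the head of the sequence: "treatment comparisons will begin with the first primary endpoint". Protocol 9.6 adds "Each test will be 2-sided and performed at the 0.05 level of significance", and a nonsignificant result stops the testing. SAP 7.2 opens secondary testing only if all three primary comparisons succeed.

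For this lead test SAP 6.2.2.2 specifies an "ANCOVA model with effects due to baseline trough morning percent predicted" FEV1, with sex, age, pooled center and previous therapy. SAP 4.2 says the 1-hour baseline "is defined as the predose percent predicted trough morning" FEV1 reading at the randomization visit, taken at the investigational center. SAP 6.2.2.2 and Protocol 9.5.4.1 place it there too.

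The home baseline is a separate quantity. In SAP 4.2 it "is defined as the average of recorded (nonmissing) percent predicted trough morning" FEV1 over the seven days before randomization, and it serves as baseline for the Fp versus placebo comparisons. In the 1-hour analysis it appears only as a substitute when the clinic value is missing or implausible.

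**The concern.** The lead test uses one morning's lung function to account for differences between children, while about a week of mornings on the same measure is already in the database. A supervised best-of-several session limits variation between blows but not variation between days, so an average over several days may say more about a child's usual level. It is measured before randomization, so adding it cannot bias the comparison. Because this test opens the sequence, extra precision here also raises the chance that the later tests are reached.

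There is a smaller problem of wording. SAP 6.2.1 gives the home average nearly the same name that SAP 6.2.2.2 gives the covariate. Protocol 9.5.4.1 uses the same covariate wording for both primary models, and the Appendix A example code calls it only `base`. Two programmers could fit different models for the lead test.

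**Working it through.** **The plan's own figure.** SAP 2.4 says "the SD was revised to 22% and the overall mean change from baseline was revised to 6.5" percent, "and the power down to 80" percent, with 181 per group, sized on an unadjusted ANOVA.

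- Sample size: n = 2 × (22 × (1.960 + 0.842) / 6.5)² = 179.8, so 180 by normal approximation.
- Power at 181: 6.5 / (22 × √(2/181)) = 2.811, and Φ(2.811 − 1.960) = 80.3% (80.0% by noncentral t).
- Dropout: 181 / 0.88 = 205.7, so 206.

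The stated 181 and 206 reproduce. The 80% takes no credit for any covariate, so it is not the power of the planned ANCOVA.

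**Model for the gain (assumptions; the documents give no variance components or correlations).** Each child has a stable level with SD s_T. The clinic predose value adds error with SD s_c. Each home morning has the same error SD, with a share ρ of its variance common to all seven days. The SD of change is held at 22 (variance 484). Sex, age, center and previous therapy are ignored.

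- Home-average error variance: s_h² = s_c² × (ρ + (1 − ρ)/7)
- Residual variance, planned model: v1 = 484 − s_c² + 1/(1/s_T² + 1/s_c²)
- Residual variance, home average added: v2 = 484 − s_c² + 1/(1/s_T² + 1/s_c² + 1/s_h²)
- Power: Φ(6.5/√(2v/181) − 1.960)

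First row in full: s_T = 8, s_c = 8, ρ = 0.5 gives s_h² = 64 × (0.5 + 0.5/7) = 36.57, v1 = 420 + 32 = 452.0 and v2 = 420 + 17.1 = 437.1.

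| s_T | s_c | ρ | v1 | v2 | Reduction | Planned power | With home average | Gain (points) |
|---|---|---|---|---|---|---|---|---|
| 8 | 8 | 0.5 | 452.0 | 437.1 | 3.3% | 82.9% | 84.1% | 1.2 |
| 12 | 8 | 0.5 | 464.3 | 440.0 | 5.2% | 81.9% | 83.8% | 2.0 |
| 10 | 12 | 0.5 | 399.0 | 374.4 | 6.2% | 87.2% | 89.2% | 2.0 |
| 8 | 15 | 0.5 | 308.8 | 294.9 | 4.5% | 94.1% | 95.0% | 0.9 |
| 12 | 12 | 0 | 412.0 | 356.0 | 13.6% | 86.1% | 90.6% | 4.5 |
| 12 | 15 | 0 | 346.8 | 282.5 | 18.5% | 91.3% | 95.7% | 4.4 |

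Over s_T of 8, 10, 12 and s_c of 8, 10, 12, 15, with ρ of 0 or 0.5, the reduction runs from 3.3% to 18.5% and the gain from 0.9 to 4.5 points. Planned power is 83% and 91% at the smallest and largest reductions, and 82% to 94% over the whole grid.

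**Wider assumptions.** With s_T 8 to 13, s_c 4 to 16 and home daily error 1.0 to 1.5 times s_c, the reduction runs from about 1% to 23% and the gain from about 0.4 to 5 points. The low end (s_T = 8, s_c = 4, ratio 1.5, ρ = 0.5) has v1 = 480.8 and v2 = 475.9, with power moving from 80.5% to 80.9%.

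**The case against.** The planned model is a legitimate choice, and one baseline term is common practice. That stands: nothing here is an error. Several stronger readings are tempting, and the documents do not support them.

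- **That the clinic baseline is documented as noisy.** The effort problems in Protocol 9.1 and SAP 2.4 came from FEV1 stability monitoring, which under Protocol 4.3.2 uses home readings. The clinic value is supervised and is the best of a session requiring several acceptable and repeatable blows (Protocol 3.1). The SD of 22 for the 1-hour change, against 17 for the home weekly average, is only indirect evidence. Both are SDs of change, and the blinded data included nonphysiologic values that SAP 4.1 now sets to missing.
- **That power rises from 80% to 81–87%.** This applies the variance reduction to the unadjusted ANOVA figure. Under the same assumptions the planned ANCOVA is already above 80%, so the gain is smaller.
- **That all three primary tests lose precision.** Tests 2 and 3 use another endpoint and a model that already contains the home average. Only their chance of being reached changes.
- **That the model adjusts for nothing else, or that every child has the home average.** Four other covariates are listed. SAP 4.2 records that a few children had fewer than five home values, and it then reaches further back or substitutes an overall value.

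Two further cautions reduce the likely gain. The 40% to 85% entry window on home FEV1 (Protocol 5.9) narrows the spread between children. Averaging also helps less if poor effort persists from day to day.

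**Conclusion.** The lead ANCOVA has one lung-function covariate, most naturally read as the clinic predose value, and leaves out a second, nearly complete pre-randomization measure. Adding it is a sound, low-cost efficiency improvement. On the stated assumptions it is worth roughly 1 to 4.5 power points, and possibly less than 1. The direction is safer than the size: if the home average adds nothing beyond the clinic value, the loss is about one degree of freedom.

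A reader might hope the covariate would rescue the power of this test; it would not. The 6.5 is labeled an overall mean change but enters the calculation as a treatment difference. At the initial planning difference ("The initial assumed common standard deviation (SD) was 9.3% and the true treatment difference was 4.5" percent), with SD 22 and 181 per group, unadjusted power is Φ(4.5/(22 × √(2/181)) − 1.960) = Φ(1.946 − 1.960) = 49.4%. A gain of a few points does not offset that.

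The naming overlap deserves correction whether or not the second covariate is adopted.

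**What to change.** Amend the SAP before unblinding:

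1. In SAP 6.2.2.2, and in the code for the 1-hour endpoint, name the baseline covariate as the clinic predose percent predicted FEV1 at the randomization visit. Keep the change score computed from that value.
2. Add the baseline weekly average home percent predicted trough FEV1, as derived in SAP 4.2, as a second continuous covariate in the 1-hour ANCOVA.
3. Add the same term to the covariate list of the 1-hour imputation model in Appendix A, so that the imputation and analysis models agree.

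The cost is one degree of freedom and a few lines of specification and code. No new data are needed, and the existing SAP 4.2 rules already supply a value for children with too few home readings. The sample size and the testing order do not change.

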6.2.2.3. Sensitivity Analyses

The following list of sensitivity analyses are prespecified for this study, to evaluate alternative estimands and assess the robustness of the primary efficacy results. Each sensitivity analysis will be conducted for the 2 primary efficacy endpoints, unless otherwise noted.

- Effectiveness with retrieved dropout data: to evaluate the estimand of the effect of the treatment regimens as actually taken (effectiveness), the analysis will be repeated including observed FEV₁ data over 12 weeks, for patients who completed the 12-week treatment period and for patients who discontinued from treatment earlier than week 12 but from whom the sponsor was able to collect efficacy data post discontinuation. Early withdrawal patients for whom the sponsor fails to retrieve data post discontinuation despite all attempts to contact the patient, a reference-based

imputation (RBI), which is an MNAR mechanism, will be utilized. The RBI method multiply imputes the missing data in every treatment group based on an imputation model built using data from the placebo group. This will yield a conservative treatment effect estimate as compared to the estimate obtained from multiple imputations (MI) under MAR (see [Appendix A](#) for details).

- **Treatment completer analysis:** In this completer analysis, the estimand is conditional on taking IMP. This estimand applies to all patients in the ITT analysis set who have completed the 12-week treatment period; patients who have taken their medication as directed without any major protocol violations. Note that since the use of incorrect IMP is considered a major treatment administration protocol violation, “as randomized” will coincide with “as treated” for the treatment assignment in this population. No imputation will be used since this is a completer analysis.
- **“Tipping point” multiple imputations:** similar to the primary estimand (change due to the initially randomized treatments as actually taken without retrieved dropout data), this sensitivity analysis will utilize multiple imputations under the MNAR assumption. For placebo patients, MAR will be assumed in all applications of multiple imputations. For the active arms, in the first application, MAR will be assumed and the imputations will be drawn from data in the corresponding active arms. In subsequent applications, shifts to the distribution of the active arms will be applied to represent different degrees of effect loss, ie, MNAR will be assumed. In this analysis, only data collected before IMP discontinuation will be utilized. If the sensitivity analysis reveals that the tipping point consists of unreasonable values, the robustness of the study results is supported. The methodology and algorithm used for imputations is provided in [Appendix B](#).
- **“2-dimensional tipping point” multiple imputations:** similar to above, the shifts to the distribution will apply to both placebo and active arms, to represent different degrees of effect loss. In this analysis, only data collected before IMP discontinuation will be utilized. An example below shows that a specified amount from actives will be subtracted from its value and at the same time, another specified amount will be added to the placebo. The methodology and algorithm used for imputations is provided in [Appendix C](#).

Table 6: An example of shift amount in percent predicted FEV₁

Placebo	Active
0	0
0	-5
0	-10
0	-15
2	-5
2	-10
2	-15

Placebo	Active
4	-5
4	-10
4	-15

Table 6: An example of shift amount in percent predicted FEV₁ (Continued)

Placebo	Active
6	-5
6	-10
6	-15

- Mixed approach of LOCF and baseline observation carried forward (BOCF): this sensitivity analysis will penalize discontinued patients who have a positive change from baseline score to zero by using (BOCF) method, thus these discontinued patients are treated as failures. While patients who discontinue IMP who have a negative change from baseline score will not have their results adjusted (LOCF) since their scores are already poor. In this imputation method, the imputed value is the lower between LOCF and BOCF for each patient. No adjustments will be made to the results for patients who complete the study. Retrieved dropout data will be included for this analysis. Details are provided in [Appendix D](#).
- MMRM: similar to the primary estimand (change due to the initially randomized treatments as actually taken without retrieved dropout data), this sensitivity analysis will be performed using a MMRM model. This analysis represents a MAR assumption. The sensitivity analysis will be performed for the first primary endpoint, ie, change from baseline in the weekly average of percent predicted trough morning FEV₁ over the 12-week treatment period. Details are provided in [Appendix E](#).

